## Study Protocol

The current study tested the impact of multiple exposures to a brief nicotine corrective messaging intervention and nicotine content of study cigarettes on nicotine beliefs and subsequent use of tobacco and nicotine products in a 28-day lab-based study of 74 adults who smoke cigarettes daily. Data were collected at the University of Pennsylvania Center for Interdisciplinary Research on Nicotine Addiction. A parallel population-based study of exposure to nicotine corrective messaging was conducted in adult smokers and non-smokers followed for 12 weeks (NCT04805515).

The lab-based study was a prospective, randomized factorial trial of nicotine corrective messaging (NCM vs. control) and nicotine content of cigarettes (normal vs. reduced) in current daily adult cigarette smokers (minimum 5 daily cigarettes for the past year, carbon monoxide (CO) at least 5 parts per million at Week 0, and no current use of other tobacco or nicotine containing products) for a 35-day protocol. Recruitment occurred through community and campus bulletin boards, local newspapers, radio and television ads, and previous participants who agreed to be re-contacted for non-cessation or non-treatment studies. At the baseline visit (Week 0), eligible, consenting participants provided a CO sample, complete demographic and smoking history measures, and measures of nicotine beliefs and intentions/use of nicotine and tobacco products (see Study Measures). They also provided breath and urine samples for biomarker assessment and continued to smoke their usual brand cigarettes to assess their baseline cigarette smoking behavior. Participants were instructed to continue smoking their own brand cigarettes and collect used filters as a verified count of daily smoking using re-sealable bags provided, while also recording their smoking in a calendar. Participants returned on Day 7 (Week 1; end of baseline), returned used cigarette filters, and were randomized to one of four groups: 1) Nicotine Corrective Messaging (NCM) + RNC cigarettes, 2) NCM + normal nicotine content (NNC) cigarettes, 3) Control + RNC cigarettes, or 4) Control + NNC cigarettes. Participants receiving normal nicotine content or reduced nicotine content cigarettes were explicitly told which product they have been given (i.e., unblinded).

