## Statistical Analysis Plan

Sample Size. Power for Aim 2 was calculated for 160 adult current daily cigarette smokers using an ANCOVA framework to detect differences between any two study conditions; with n=40 in each of the four conditions in the trial, we will have 80% power to detect medium effect sizes (Cohen's  $f = 0.33$ ) in continuous outcomes (i.e., nicotine beliefs, behavior, subjective ratings), assuming three covariates in the model (i.e., age, gender, cigarettes per day at baseline). In addition, using a two-way analysis of variance framework, 40 participants in each study condition provides 85% power to detect a statistically significant moderation of these same outcomes by the nicotine content of the study cigarettes, assuming that the responses by those in the NCM + NNC condition differ from those in the other three conditions by 1 standard deviation. Sample size for the eye tracking analyses is based on our earlier work that recruited 200 participants to a 2 x 2 factorial design and used the same outcomes (i.e., dwell time, time to first area of interest).

Data Preparation. We will conduct data screening steps similar to Aim 1 including assessing outliers, missing data presence/patterns, and normality/equality of variance assumptions. Non-normal data will be transformed as needed. In all analyses, the assumptions underlying the application of all the statistical methods that are used will be examined, principally using standardized residuals, influence diagnostics, and graphical displays. Where needed, appropriate transformations will be applied to ensure that data meet model assumptions. Descriptive analyses will characterize participants overall and by study condition. Aim 2 eye tracking data will be cleaned and pre-processed using standard procedures from our previous work. Descriptive analyses will characterize participants overall and by study conditions. Bivariate tests will assess for differences in participant characteristics by conditions and examine if any baseline variables that are imbalanced between study groups are associated with primary and secondary outcomes ( $p < .10$ ). Any such variables will be accounted for in analyses as covariates.

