For the second area (*mediation*), we will draw from traditional mediation frameworks and use robust methods to explore the relationships outlined in our theoretical framework and whether changes in nicotine beliefs post-exposure (Weeks 2, 3, 4) influence nicotine-related attitudes, norms, behavioral control, intention, and behavior at the final assessment (Week 5). To complement Aim 1 analyses, we will examine whether nicotine beliefs at Week 2 are associated with these Week 5 outcomes using bivariate statistics and the general linear model-based analysis accounting for any covariates as described above. Where these preliminary steps indicate potential correlation between nicotine beliefs and study outcomes ( $p < .05$ ), we will test for mediation by estimating the indirect effects of nicotine beliefs on follow-up outcomes via the study condition using a bias-corrected bootstrapping method with 1,000 resamples. This approach estimates indirect (i.e., mediation) effects and produces bias-corrected asymmetric 95% CIs correcting for non-normality of the distribution of indirect effects and providing higher power and better control over the Type I error rate versus traditional approaches to test mediation. Asymmetric 95% confidence intervals around indirect effect estimates for nicotine beliefs that do not include zero will be interpreted to indicate significant mediation.

For the third area (*visual attention*), we will identify the regions of interest (ROIs) in each nicotine education message based on responses to the Aim 1/Wave 1 heatmap task. Using eye-tracking, we will explore whether attention to the ROIs (i.e., dwell time, fixations) is correlated with scores on the nicotine beliefs scales (i.e., nicotine, NRT, e-cigarette, RNC cigarette beliefs) at the same assessment (Weeks 1-4). Given the content of messages in the nicotine education condition, we will be able to assess whether attention to specific ROIs is correlated with specific beliefs (i.e., whether attention to a specific ROI within the “Nicotine does not cause cancer” is correlated with response to the nicotine belief item regarding nicotine causing cancer). We will also be able to explore the prospective relationship between visual attention to the nicotine

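### The mediation bootstrap is justified by better Type I error control, yet its error is about 6.5–8.5% at N=74 when messaging leaves beliefs unchanged and beliefs predict the outcome

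*Combined protocol and SAP*

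**What the plan says.** The mediation paragraph of the SAP (Analytic Approach) works in two steps. Week 2 beliefs are first related to each Week 5 outcome "using bivariate statistics and the general linear model-based analysis accounting for any covariates as described above". Only outcomes that reach p<.05 in that step go on to a test of the indirect effect, which is made by "a bias-corrected bootstrapping method with 1,000 resamples".

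The decision rule is: "Asymmetric 95% confidence intervals around indirect effect estimates for nicotine beliefs that do not include zero will be interpreted to indicate significant mediation". The method is justified as "providing higher power and better control over the Type I error rate versus traditional approaches to test mediation". No error rate, path size or simulation is given in support.

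The Study Protocol describes a "28-day lab-based study of 74 adults who smoke cigarettes daily", while the sample-size paragraph plans "with n=40 in each of the four conditions in the trial", that is 160. Both sizes are used below.

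**The concern.** A bias-corrected interval moves its percentile cut-offs according to the share of resampled indirect effects that fall below the estimate. When one path is zero and the other is not, this tends to push the interval away from zero, so a nominal 95% interval can exclude zero in more than 5% of null trials. The SAP claims the opposite property.

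The case that matters in practice is a false claim that messaging works through beliefs: beliefs track attitudes, norms and intentions as they would in any sample, but messaging has not moved beliefs. The SAP screen looks only at the belief-to-outcome association, so it cannot catch this case. The screen may also remove outcomes with true mediation, because a direct effect of opposite sign weakens the raw correlation on which it may rest.

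**Working it through.** The plan states no error rate or power for mediation, so there is no figure to reproduce.

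**Model.** X is messaging condition (0/1, balanced 1:1), M = aX + e is beliefs, and Y = bM + c'X + e is the outcome, with unit residual SDs and normal errors. The documents give none of a, b or c'; all values are assumptions. Intervals use 1,000 resamples as planned, with 8,000 simulated trials per tabulated cell. The Monte Carlo SE at 7.8% is √(0.078 × 0.922 / 8000) = 0.3 points.

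**False-positive rate, c' = 0.** BC is the bias-corrected interval. The screened column counts trials that pass the screen and are declared significant; a range runs from a bivariate to a condition-adjusted screen. The last three columns are unscreened.

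| N | a, b | BC, no screen | BC, screened | Percentile | Joint significance | Sobel |
|---|---|---|---|---|---|---|
| 74 | 0, .39 | 7.8% | 7.6% | 4.7% | 4.4% | 1.8% |
| 74 | 0, .59 | 7.7% | 7.7% | 5.8% | 5.0% | 3.5% |
| 74 | .5, 0 | 5.7% | 2.7–3.1% | 2.6% | 2.7% | 0.5% |
| 74 | .8, 0 | 8.2% | 3.7–4.6% | 5.3% | 4.8% | 1.9% |
| 74 | 1.0, 0 | 8.3% | 3.5–4.8% | 5.8% | 5.1% | 2.9% |
| 160 | 0, .39 | 7.1% | 7.1% | 5.0% | 4.7% | 3.0% |
| 160 | .8, 0 | 7.7% | 3.8–5.1% | 6.0% | 5.2% | 3.5% |

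At N=160 with a=0, b=.59, BC is about 6.2% (2,500 trials). A separate run of the two a=0 cells at N=74 gave BC 6.7% (b=.39) and 8.5% (b=.59), 6.5% and 8.5% after the screen, and percentile 3.9% and 6.6%. The ranges quoted span both runs.

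**Why the screen helps in one case only.** With a=0, the bivariate screen passes 90.2% of trials at b=.39 and 99.8% at b=.59. It removes only 0.2 and 0.01 points of error. With b=0 and no direct effect it passes about 5%, which caps the error near 5%.

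**Power at a=.8, b=.39, c'=0, N=74, no screen.** BC 89%, percentile 83–84%, joint significance 84%, Sobel 70%.

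**Cost of the screen.** Var(M) = 0.8² × 0.25 + 1 = 1.16. Cov(M,Y) = b·Var(M) + c'·a·0.25. Var(Y) = (ab + c')² × 0.25 + b² + 1. The chance of passing a bivariate screen is about Φ(atanh(r)·√71 − 1.96).

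- c' = 0: Cov = 0.4524, Var(Y) = 1.1764, r = 0.387, pass about Φ(1.48) = 93%.
- c' = −0.5: Cov = 0.4524 − 0.1 = 0.3524, Var(Y) = 1.1609, r = 0.304, pass about Φ(0.68) = 75%.

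In simulation with c' = −0.5, percentile power falls from about 84% to 71% with a bivariate screen, but only to 82% if the screen adjusts for condition. With c' = 0 the percentile loss is at most 2 points under either screen.

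**The case against.** **The rate depends on unknown paths.** A reader might infer that the method runs at 7–9% at this sample size whatever the truth. The documents do not support that. They give no path sizes, and unscreened BC error at N=74 is 0.6% with both paths null, 2.4% at a=0, b=.14 and 3.3% at a=.3, b=0. Among outcomes that pass a bivariate screen the rate was 7.4% to 9.0% for b from .14 to .59 (3,000 trials per cell), but that is conditional on passing and still requires a=0 with b above zero. This objection stands and limits the point.

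**The screen already protects when b=0.** True. There the screened BC rate is at or below about 5%, and an unscreened percentile interval (5.3–5.8% at a=.8 and 1.0) does no better. The change helps only when a=0.

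**A false claim would sit beside a null primary result.** Path a is the effect of messaging on beliefs, the primary outcome. In one check, 2.7–2.9 points of a 6.9–8.0% error came from trials where the test of path a itself had p>.05, roughly the whole excess over 5%. An alert reader could see the conflict, but the decision rule does not require path a to be shown.

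**Sobel is also far from 5%.** At b=.39 it misses by 3.2 points (1.8%) and BC by 2.8 (7.8%). But Sobel errs on the safe side, and joint significance is close to nominal. The SAP's claim of higher power is correct (89% against 70%).

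**The screen may include condition.** A reader might infer that it ignores study condition. The SAP refers only to covariates described above and does not say whether messaging condition is among them, so the larger power loss is conditional. Nor do the documents hypothesise an opposing direct effect.

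**Conclusion.** The statement of better Type I error control is wrong as written for the case a=0 with moderate or large b: about 6.5–8.5% at N=74 and about 6–7% at N=160, with or without the plan's screen. It does not extend to null or weak paths, nor to b=0 once the screen is applied.

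The loss of true mediation to the screen is a secondary point. About 13 points of power (84% to 71%) are lost only if the screen is bivariate and a direct effect of about −0.5 SD opposes the indirect one; a condition-adjusted screen loses about 2.

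These figures rest on assumed paths, normal errors, one balanced two-level exposure and no covariates, whereas the SAP elsewhere treats study condition as four arms. No primary or secondary conclusion depends on this analysis, so severity is low.

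**What to change.** 1. Replace the bias-corrected interval with the percentile bootstrap interval for the indirect effect. This is one software option, at a cost of about 5 points of power in the scenario above (89% to 84%).
2. Delete the statement that the bias-corrected method controls Type I error better.
3. Report the indirect effect and its interval for every listed construct (attitudes, norms, behavioral control, intention, use) without the correlation screen. If the screen is kept, state its model and include messaging condition in it.

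Dropping the screen means more estimates. If each of the four belief scales named in the visual-attention paragraph is a mediator for each of five constructs, there are 4 × 5 = 20 intervals, so the report should label them exploratory and unadjusted for multiplicity. Raising the resamples from 1,000 to 5,000 is optional; nothing here shows that the number of resamples causes the excess.

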The Nicotine Corrective Messaging (NCM) intervention condition was based on messages tested in our team's pilot study. It included six original messages and two new messages addressing nicotine in cigarette and e-cigarette products that were adapted from several evidence-based sources to be more accessible to a lay audience. The sources consisted of FDA's 2017 comprehensive plan for tobacco and nicotine regulation, FDA's 2013 modifications to labeling of NRT products for over-the-counter human use, the 2014 U.S. Surgeon General's Report on the Health Consequences of Smoking, reports on carcinogens from the International Agency for Research on Cancer, and the NASEM report on the "Public Health Consequences of E-cigarettes." Participants in the NCM condition were exposed to all eight messages in the same order at each exposure.

Participants in the NCM condition received their first exposure to the study messages on Day 7 in the lab. Eye tracking was assessed during a five-second exposure to each educational message, equating to a minimum 40-second exposure. At the end of the session, all participants left with study-provided cigarettes to last until the next visit. Participants continued to collect used filters and record daily number of study cigarettes, non-study cigarettes, and other nicotine or tobacco products used each day for the duration of the study. At lab visits on Days 14 (Week 2), 21 (Week 3), and 28 (Week 4), daily nicotine/tobacco use calendars and used filters were collected at the start of the visit. At the Week 2 visit, all participants completed the first post-exposure measures of nicotine beliefs and intentions/use of nicotine and tobacco products. In visits at Weeks 2-4, participants smoked their study product with CO collected at the start and each smoking session videotaped to extract smoking

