## Study Measures

	Aim 1: Population study	Aim 2: Lab study
Intervention/Exposure		
Nicotine messaging vs. control	Wave 1	Week 1
Normal nicotine vs. RNC cigarette		Week 1
Heatmapping	Waves 1-4	
Perceived message effectiveness	Wave 4	Week 5
Message credibility	Wave 4	Week 5
Eye-tracking		Weeks 1-4
Biomarkers		Weeks 0, 5
Outcomes		
Nicotine beliefs	Waves 1, 2, 4	Weeks 0, 2, 5
Intention to use nicotine/tobacco products	Waves 1, 2, 4	Weeks 0, 2, 5
Nicotine/tobacco use and behavior	Waves 1, 2, 4	Weeks 0, 2, 5
Subjective rating of study cigarette		Weeks 1-5
Manipulation check	Waves 1, 2, 4	Weeks 0, 2, 5
Moderators		
Sociodemographics	Wave 1	Week 0
Literacy	Wave 1	Week 0
Cancer risk beliefs	Wave 1	Week 0
Cancer risk behaviors	Wave 1	Week 0
Fagerstrom test for nicotine dependence	Wave 1	Week 0
Other key constructs		
Attitudes about nicotine	Waves 1, 2, 4	Weeks 0, 2, 5
Nicotine-related norms	Waves 1, 2, 4	Weeks 0, 2, 5
Behavioral control	Waves 1, 2, 4	Weeks 0, 2, 5
Stages of change	Wave 1, 4	Week 0, 5
Policy support	Wave 4	Week 5

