whether using study cigarettes with a known nicotine content (i.e., normal or reduced) moderates the effect of NCM on our primary and secondary outcomes by incorporating an interaction between NCM condition (NCM/control) and study cigarette condition (NNC/RNC) through the following steps: 1) bivariate analyses, to determine if outcomes vary by these variables; 2) testing whether study cigarette condition moderates ( $p < .05$ ) experimental effects in the models above; if so, performing post-hoc statistical testing to examine the direction and magnitude of the moderation; 3) if no evidence of moderation exists, including study cigarette condition as a covariate.

Our previous work highlights that assessing perceptions of RNC cigarettes that find an association between participants perceiving that their assigned product is low nicotine and reporting lower harm perceptions of the product. To address **Hypothesis 2b**, we will also use autoregressive, cross-lagged panel analysis to examine the direction of the relationships between subjective ratings and nicotine beliefs over three timepoints (Weeks 0, 2, and 5) and whether the regression paths vary in magnitude by study condition.

As in Aim 1, our exploratory analyses will focus on three areas: 1) potential moderators of the relationship between intervention condition and the study outcomes; 2) nicotine beliefs as a potential mediator of the relationship between intervention condition and constructs identified in the Theory of Planned Behavior (i.e., nicotine-related attitudes, norms, behavioral control, and nicotine/tobacco intentions and use); and 3) the relationship between visual attention to nicotine education messages and nicotine beliefs in the participants exposed to the NCM intervention.

For the first area (*moderation*), we will conduct exploratory analyses using the same steps described for Hypothesis 2a to determine whether there are potential moderators of the relationship between the study condition (NCM + RNC, NCM + NNC, Control + RNC, Control + NNC) and outcomes, specifically age, gender, baseline cancer beliefs and cancer risk behaviors.

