education messages (e.g., duration spent viewing messages, attention to ROIs) and nicotine beliefs and whether there are differences in visual attention in the NCM intervention condition over the four weeks of data collection. These data will inform potential refinements to nicotine education messages for future studies.

Missing data: The most effective approach to eliminating biases and inefficiency caused by missing data is to collect complete data. In both aims of our study, we will use several tools available to maintain contact and verify that forms are complete. Use of computerized survey platforms (e.g., Qualtrics) in this study will provide additional mechanisms to improve completeness of survey responses, but even so, some participants may refuse to answer certain questions. We anticipate that one cause of missing data will be item non-response on self-report questionnaires; another will be missing assessments. Finally, missing data can arise through attrition; however, the steps outlined in the proposal are meant to minimize this. The general/generalized linear mixed model that we will be using for analysis for Aim 2 is a maximum likelihood approach to repeated measures analysis of variance that does not rely on imputation, which may give differing results depending upon the exact imputation procedure used. Rather, this approach estimates the parameter values that would maximize the probability of observing the data collected. In the event of missing variables, the likelihood for a given individual is the probability of observing the non-missing variables. Thus, the maximum likelihood approach allows the use of data from subjects for the time period for which data is available, but not for time periods for which the data is missing. This procedure uses information from earlier time periods to estimate the effects of later time periods, while also accounting for the uncertainty of the projection in the computation of standard errors and test statistics. Maximum likelihood estimation is considered superior to imputation methods for the treatment of missing data in clinical trials.

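### The exploratory visual-attention analysis correlates non-randomised attention with beliefs and pre-specifies no adjustment for prior belief or literacy, so either could produce the association

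*Combined protocol and SAP*

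**What the plan says.** The Analytic Approach section of the SAP lists as its third exploratory area "the relationship between visual attention to nicotine education messages and nicotine beliefs in the participants exposed to the NCM intervention". Three analyses follow.

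- Scale level: "we will explore whether attention to the ROIs (i.e., dwell time, fixations) is correlated with scores on the nicotine beliefs scales", at the same assessment.
- Item level: "we will be able to assess whether attention to specific ROIs is correlated with specific beliefs".
- Over time: "We will also be able to explore the prospective relationship between visual attention to the nicotine" messages and beliefs. No model is given for this one.

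None of the three names a covariate, whereas the mediation paragraph just before them does refer to covariate adjustment. The area closes with its intended use: "These data will inform potential refinements to nicotine education messages for future studies".

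The Study Measures table shows that the relevant baseline variables are collected: "Literacy Wave 1 Week 0" (listed under moderators) and "Nicotine beliefs Waves 1, 2, 4 Weeks 0, 2, 5". On exposure, the Study Protocol section says of the first session that "Eye tracking was assessed during a five-second exposure to each educational message".

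The only general covariate rule is under Data Preparation. It adjusts for baseline variables that differ between study conditions and are also related to outcomes (p < .10).

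**The concern.** Randomisation protects the comparison of NCM with control. It does not protect a comparison, within NCM, of people who looked longer with people who looked less. What someone already believes about nicotine can affect where they look, and it will usually predict what they report later. Reading ability may act in the same way when a message is viewed for a few seconds. A plain correlation cannot separate these routes from an effect of attention on belief.

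The covariate rule does not fill the gap, because it answers a different question. Literacy or Week 0 belief could be perfectly balanced across the four conditions, and so fail the screen, yet still be related to both attention and belief among NCM participants.

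At stake is what the message developers conclude. If attention to one region tracks a belief only because people who already held that belief looked there, the region may be credited with an effect that it did not have.

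**Working it through.** **No figure to reproduce.** The plan gives no alpha, power or detectable correlation for this analysis. Its eye-tracking sample size rests on an earlier study of 200 participants.

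**Inputs from the documents**
- Planned NCM participants: 2 conditions × 40 = 80 (SAP, Sample Size).
- Participants reported: 74 (Study Protocol). Assuming an equal split, 74 / 2 = 37 in NCM.

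**Inputs assumed**
- Correlation of the confounder with attention and with later belief: 0.2 to 0.5 each. The documents give no values.
- No true effect of attention on belief; two-sided test at 0.05.

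**One confounder.** Spurious r = r(attention, confounder) × r(belief, confounder). By Fisher's z, with δ = atanh(r) × √(n − 3), the rejection rate is Φ(δ − 1.96) + Φ(−δ − 1.96).

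| Assumed correlations | Spurious r | n = 37 | n = 80 |
|---|---|---|---|
| 0.2 and 0.2 | 0.04 | 5.6% | 6.4% |
| 0.3 and 0.3 | 0.09 | 8.2% | 12.4% |
| 0.5 and 0.5 | 0.25 | 31.9% | 61.1% |

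Example, last row, n = 37: atanh(0.25) = 0.255; × √34 gives δ = 1.49; Φ(−0.47) = 0.319, and the second term is negligible.

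The rate rises with n because the bias stays fixed while the standard error shrinks. A larger sample does not cure it.

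**Two confounders together (illustration).** Let literacy and Week 0 belief each correlate 0.3 with attention, 0.3 and 0.5 respectively with later belief, and 0.2 with each other. Then spurious r = 0.3 × (0.3 − 0.2 × 0.5)/0.96 + 0.3 × (0.5 − 0.2 × 0.3)/0.96 = 0.0625 + 0.1375 = 0.20. The rejection rate is 22% at n = 37 and 43% at n = 80. A simulation of 10,000 runs gave 22% and 44% unadjusted, and 5.4% and 4.9% after adjusting for both.

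**Which visits can be used.** Attention is recorded at Weeks 1-4 and beliefs at Weeks 0, 2 and 5, so Week 2 is the only visit with both. The Study Protocol section appears to place the Week 2 belief measures before that visit's message exposure. A same-visit correlation at Week 2 could therefore run from belief to attention. It also means that Week 2 belief precedes attention at Weeks 2-4 and can confound its relation with Week 5 belief. Adjusting that relation for Week 0 belief alone would not be enough.

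**The case against.** The strongest reply is that the area is labelled exploratory and worded as correlation, with no causal estimand, threshold or decision rule. An unadjusted association is a legitimate descriptive result. This stands, and it limits the severity. A reader might infer from the closing sentence on message refinement that the plan states a causal use. It does not; it says only that the data will inform refinements. The case for adjustment is that the result becomes more useful for that purpose.

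A reader might also infer that literacy is shut out of every analysis. The documents do not support that. No SAP analysis names literacy, and the moderators to be examined omit it, but as a Week 0 variable it could enter through the Data Preparation rule. Adjustment is not assured, rather than ruled out. For the analysis over time no model is stated, so the lack of adjustment there is read from silence.

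The literacy route is plausible but not documented. The plan does not say what its literacy measure captures or that the ROIs are text. The five-second exposure is stated for Day 7 only, and the eight messages are repeated at later visits. Even the direction is unknown, since slower readers might dwell longer. General literacy would also tend to shift many ROI correlations together rather than single out one region. These points stand, and they make prior belief the firmer half of the concern.

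Finally, the rejection rates depend on assumed correlations, and weak confounding leaves the rate near nominal. That is so; they illustrate the possible scale and are not properties of this plan.

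**Conclusion.** The concern holds as a modest improvement to an exploratory analysis. The plan relates non-randomised attention to beliefs within NCM participants without pre-specified baseline adjustment, and its general covariate rule cannot be relied on to supply it. Prior belief, and possibly literacy, could therefore generate an association.

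The size cannot be derived from the documents. Under the assumed range for one confounder, the false-positive rate lies between about 6% and 32% at n of about 37, or about 6% and 61% at n = 80, against a nominal 5%. The lower end is nearly harmless. The primary and secondary randomised comparisons are unaffected.

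**What to change.** In the visual-attention paragraphs of the SAP, make two regressions within NCM participants the main analysis:

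1. Week 2 belief on Week 1 attention, adjusting for the Week 0 score on the same scale, Week 0 literacy and assigned cigarette type.
2. Week 5 belief on Weeks 2-4 attention, adjusting for both the Week 2 and the Week 0 score on the same scale, plus literacy and cigarette type.

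Report each attention coefficient with its CI. Keep any unadjusted correlations as descriptive only. Label all results exploratory and associational, because unmeasured confounding may remain.

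The cost is SAP wording and 3 df in the first model or 4 in the second, taking literacy as a single score. With one attention term and 37 participants, that leaves 37 − 5 = 32 and 37 − 6 = 31 residual df. Every covariate is already collected or assigned.
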